#### After randomization:

- Provide medication and instructions based on the treatment arm randomized to
- Provide the group algorithm to both patient and provider.

Once the participant is randomized, the treatment algorithms will be conspicuously placed in the patient's medical record (whether electronic or paper medical record is utilized) such that providers will be aware of treatment plan at all times.

In both groups, serial CBC follow up and survey for symptoms will be assessed. Baseline data consisting gestational age of pregnancy, body mass index, pre-pregnancy weight and other prenatal data including baseline BP at the randomization visit will be included. Patients will be assigned to treatment groups by a concealed randomization allocation sequence using REDCap.

The categories of patients randomized:

Patients consenting to the study will be randomized 1:1 to two treatment groups

Group 1: Patients randomized to the IV iron group will receive treatment as follows:

- Women with Hgb 9-10.9 g/dL will receive one dose of 510 mg IV ferumoxytol
- Women with Hg 7-8.9 d/dL will receive two doses of ferumoxytol 510 mg 3-8 days apart for a maximum of dose of 1020 mg (see **Figure 2**).
- Patients will receive 650mg of Tylenol prior to initiation of the infusion
- The ferumoxytol is administered as an infusion for approximately 15-30 minutes. Patients will receive the IV iron at Stanford's Clinical and Translational Research Unit (CTRU) outpatient clinics with vitals collected before infusion and monitoring for 30minutes after infusion. Alternatively, patients who are admitted to the antepartum unit may receive the infusion inpatient.

For the IV iron group, follow up labs will be performed at 4 and 8 weeks after completion of infusion/s;

Group 2: The standard of care oral iron group will be prescribed 1-2 ferrous sulfate 325 mg tablets to be taken by mouth **every other day** until delivery. Dosage will be as follows for standardization:

- one ferrous sulfate tablet every other day if Hg 9-10.9 g/dL, and
- two tablets once every other day if Hg 7-8.9 g/dL.
- Oral medications will be dispensed by the CTRU or by the Outpatient Investigational Pharmacy (final confirmation pending contracts)
- Follow up labs will be drawn for both groups. For the oral iron group, it will be drawn 4- and 8-weeks post initiation of treatment

Patients in both groups will complete post-intervention surveys at 1 week, 4 weeks, and 8-12 weeks after initiating therapy to monitor symptoms and adverse events.

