# 12.3 Analyses

We will conduct an intent-to-treat analysis to compare the primary and secondary outcomes between the treatment arms. The primary outcome is the mean change in hemoglobin in oral vs IV iron over 4 weeks as well mean change in hemoglobin pre delivery. The primary outcome will be assessed using t-tests. Baseline characteristics between the groups will be compared using t-tests and chi-square tests. If there is an imbalance between the treatment arms, we will use multivariable regression modeling. Differences will be considered statistically significant at P<0.05.

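### The primary test is an unadjusted t-test and no stratification is described, although baseline hemoglobin band sets the dose in both arms; adjustment for it should be pre-specified

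*Combined protocol and SAP*

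**What the plan says.** Allocation is covered under After randomization in Section 6: "Patients consenting to the study will be randomized 1:1 to two treatment groups", and "Patients will be assigned to treatment groups by a concealed randomization allocation sequence using REDCap". No readable section names strata, blocks or minimization. Section 4.3 sets a target of 40 women per arm.

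The same part of Section 6 ties dose to baseline hemoglobin in both arms, and Section 6.2 repeats it:

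- IV arm: "Women with Hgb 9-10.9 g/dL will receive one dose of 510 mg IV ferumoxytol", while women at 7-8.9 g/dL "will receive two doses of ferumoxytol 510 mg 3-8 days apart".
- Oral arm: "one ferrous sulfate tablet every other day if Hg 9-10.9 g/dL", and "two tablets once every other day if Hg 7-8.9 g/dL".

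The band is known in time, because Section 6 has the baseline labs reviewed before randomization. The baseline variables then listed (gestational age, body mass index, pre-pregnancy weight, blood pressure, other prenatal data) do not name hemoglobin.

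The primary outcome in Section 12.3 is mean change in hemoglobin, over 4 weeks and before delivery. On the analysis: "The primary outcome will be assessed using t-tests". On covariates: "If there is an imbalance between the treatment arms, we will use multivariable regression modeling". No covariate is named, and nothing says what counts as an imbalance.

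**The concern.** The band could matter to the outcome in two ways. It decides whether a woman gets one or two units of iron treatment in either arm, and it is a coarse version of the baseline value from which the change is measured. Women who start lower may well gain more, although the documents do not quantify this.

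In 80 women the smaller band can split unevenly by chance. Nothing described in the allocation prevents that, and the planned test does not remove its effect on the estimate. The regression that could remove it is used only if someone judges, after seeing the baseline data of an open-label trial, that the arms differ. At stake are precision in a small trial and a clear statement of which analysis is primary.

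**Working it through.** **The plan's own figure.** Sections 4.4 and 12.2 state 32 women per arm for a proportion (hemoglobin below 11 g/dL at birth hospitalization). The two proportions are not given, so 32 cannot be reproduced. It does not enter the check below, which concerns the mean change tested in Section 12.3.

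**Inputs from the documents.** 40 per arm (Section 4.3); expected gains of 0.8 versus 0.5 g/dL at 4 weeks, difference 0.3, and 1.5 versus 1.0 g/dL at birth admission, difference 0.5 (Sections 3.1 and 5.9); P<0.05 (Section 12.3).

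**Assumed inputs, not in the documents.** Lower-band share p = 20% (range 10-30%); difference in gain between bands g = 1.0 or 0.5 g/dL; within-band SD σ = 0.8 g/dL.

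**1. How uneven the split can be.** With K lower-band women among 80 split 40:40, the number in one arm is hypergeometric.

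| K | P(arms differ by 4 or more) | P(differ by 6 or more) |
|---|---|---|
| 16 | 0.40 | 0.16 |
| 24 | 0.47 | 0.22 |

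With only 8 such women, the chance of a gap of 4 or more is 0.26.

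**2. What a gap does to one trial's estimate.** Shift = (gap/40) × g. For a gap of 4 and g = 1.0 it is 0.10 g/dL, a third of the 0.3 g/dL effect at 4 weeks and a fifth of the 0.5 g/dL effect at birth. With g = 0.5 it is 0.05 g/dL.

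**3. What it costs in precision.** The standard error of the t-test already contains this variation.

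- Unadjusted variance = 2[σ² + g²p(1−p)]/n. For g = 1.0: 2(0.64 + 0.16)/40 = 0.0400, SE 0.200. For g = 0.5: 2(0.64 + 0.04)/40 = 0.0340, SE 0.184.
- Adjusted for band, allocation unstratified: about (2σ²/n)(1 + 1/(N−3)) = 0.0320 × (1 + 1/77) = 0.0324, SE 0.180.

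**4. Power for a true difference of 0.5 g/dL.** Approximately Φ(0.5/SE − 1.99), where 1.99 is the two-sided 5% critical value of t.

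| Difference in gain | Unadjusted | Adjusted |
|---|---|---|
| 1.0 g/dL | Φ(2.50 − 1.99), about 69% | Φ(2.78 − 1.99), about 78% |
| 0.5 g/dL | Φ(2.71 − 1.99), about 76% | about 78% |

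With g = 1.0, the unadjusted figure is about 73% at a 10% share (variance 2(0.64 + 0.09)/40 = 0.0365) and about 67% at a 30% share. With 64 evaluable women (80 less 20%) and a 20% share, simulation gives about 59% against 69% for g = 1.0, and 67% against 68% for g = 0.5.

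**5. Simulation of the same model (6,000 trials per scenario).** At 80 women, p = 20% and g = 1.0, unstratified allocation with the plain t-test gave a mean estimate of 0.50 for a true 0.50. Over all scenarios its type I error was 4.6-5.5%. Empirical SEs were 0.201 unadjusted and 0.181 adjusted. Power with adjustment was about 79% whether or not allocation was stratified. Stratified allocation followed by a plain t-test had type I error of 2.3-4.3%, so that test is conservative.

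**6. Would the conditional regression step in?** Section 12.3 gives no trigger. If it were the baseline chi-square test at 0.05 (assumption, no continuity correction), a 4-woman gap gives p = 0.26 (10 versus 6) or 0.33 (14 versus 10). A 6-woman gap gives p = 0.09 (11 versus 5) or 0.14 (15 versus 9). None would trigger it. A gap of about 8 to 10 would be needed, which has a probability of roughly 3-5%.

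**The case against.** The strongest case against is that randomization already deals with this. The t-test is valid without stratification, and its standard error covers chance imbalance in the band. Setting a 0.10 g/dL shift beside a 0.3 g/dL effect, without the standard error of about 0.20, makes the problem look larger than it is. All of that stands. A reader might infer bias or an inflated false-positive rate; neither follows.

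A reader might also infer that allocation is simple randomization. The documents do not say so. They are silent on method, the target of 40 per arm is compatible with blocking, and the figure for Algorithm A (Randomization) at the end of Section 6.3 is not in the text available for review. The most that can be said is that no stratification or blocking is described.

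A third tempting step is that an uneven band would set off the switch to regression. Since the trigger is undefined this cannot be asserted, and on the most natural reading gaps of 4 to 6 women would not set it off.

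Finally, the size rests on assumptions. No section gives the lower-band share or shows that the bands respond differently; Section 4.2 says only that dosing by hemoglobin level is of interest. With a 0.5 g/dL difference in gain the benefit is about two points of power, and Section 3.1 calls the trial a pilot. This limits the severity. It does not argue for leaving out a covariate that costs nothing to include.

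**Conclusion.** The point holds as a low-severity improvement. A variable that sets the dose in both arms, and is cut from the outcome variable itself, is neither described as a stratification factor nor named in the primary model. The only adjustment foreseen depends on a judgement that the plan does not define.

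The consequence is avoidable random error. On the assumed inputs, adjustment is worth about nine points of power if the bands differ by 1.0 g/dL in gain and about two points if they differ by 0.5. If they do not differ at all, it gains nothing and costs one degree of freedom. Nearly all the benefit comes from the model term, so the essential change belongs in Section 12.3 and not in the allocation table.

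**What to change.** In Section 12.3, replace the t-test and the conditional regression with one pre-specified linear regression of hemoglobin change on treatment arm and baseline hemoglobin (or hemoglobin band, 7-8.9 versus 9-10.9 g/dL). Use it at both primary time points and regardless of observed balance. List baseline hemoglobin among the baseline variables in Section 6. The cost is a few lines of text and one degree of freedom; no extra patients or tests are needed, since the value is already required for eligibility.

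In Section 6, state how the REDCap sequence is generated.

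Optionally, for women not yet randomized, stratify the allocation by the same band with concealed blocks of varying size. This means rebuilding one allocation table and accepting a possible small overall imbalance from incomplete blocks. If this is done, the band itself must be in the primary model, because a plain t-test would then be conservative.

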# 1.1.2 Responsibilities

The responsibilities of these individuals are described briefly here:

PI and co-PIs are responsible for ensuring the proper conduct of the study clinic site including recruitment as specified in the protocol and accurate collection of the data. Other specific duties include:

- a. Obtaining and maintaining IRB approval and training for study personnel
- b. Obtaining sufficient study areas for study personnel to interview patients and perform study procedures, including storage of study medication and other study supplies.
- c. Participate in study- related meetings or conference calls
- d. Familiarity and training for REDCap based data entry system by appropriate staff.
- e. Screen potential participants for eligibility and consent them. It is important to ensure the patient's primary obstetric provider agrees to follow the study treatment protocol during pregnancy.
- f. Randomize per protocol to intervention arms both arms to receive medication
- g. Follow participants during the antepartum, delivery and 6 (4-12) weeks postpartum periods: with labs as indicated in the protocol and with pre- and post-intervention surveys to monitor patient symptoms and adverse effects

- h. Facilitate collection of labs at 24-28 weeks gestation (preferred window, but may collect up to 34 complete weeks), labs at 4 and 8 weeks post-initiation of pill for standard group and post-treatment of intravenous iron in the active group and delivery.
- i. Trained research staff will conduct research data abstraction from patient medical records, and conduct participant interviews, pill counts, and other direct participant contact as required by the protocol. Research staff at CTRU, will undergo training to ascertain response to severe adverse outcomes, specifically identification of hypersensitivity reactions to intravenous iron.
- j. Investigators will participate in blinded review of outcomes in order to confirm the primary and other key outcomes.
- k. Maternal outcomes will be ascertained through 6 weeks including a postpartum visit in this window. If unscheduled visits occurred at another facility, obtain medical records release (if one has not already been obtained) to order hospital visit records.

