#### **5.6 Informed Consent Process**

An informed consent must be obtained before entry into the randomized trial. Full disclosure of the nature and potential risks of participating in the trial including the risks of being in the standard care group will be made. All potential participants will undergo the informed consent process as approved by the Institutional Review Board at each participating center. Any woman who is potentially eligible will be told about the study and asked if she is willing to participate. The point in the screening process at which a signed informed consent is required will be prior randomization. The study personnel conducting the informed consent process should emphasize the following study criteria during the informed consent process:

• Patients eligible based on hemoglobin will be offered iron studies if it's not already collected as part of routine prenatal care.

- Randomization to a treatment arm with iron to increase hemoglobin, with 50% chance to be assigned to either arm:
  - One group will receive oral iron
  - One group will receive intravenous iron
- Participants to sign medical release
- American College of Obstetrics and Gynecology recommends oral iron as standard of care and IV iron only for a select few medical indications
- Labs will be drawn 4 and 8 weeks post-initiation (Oral iron)/ post treatment (IV iron) and to evaluate anemia
  - Update: We will no longer perform study draw at 6 weeks postpartum, however, we will document labs performed as part of routine study care postpartum.
- Follow up to occur at clinic appointments or phone/email to evaluate symptoms associated with either treatment

Due to elevated rate of anemia in the Hispanic/Latinx/Latina population we will also have consents available in Spanish, or translators will be available for the consent process. A short form consent may also be used depending on the participant's preferred language.

All women who are considered for participation in the study (consent, decline or ineligible) should have a data entry form and entered into the electronic data system even if not randomized. Women who do not meet IDA criteria at 24-28 weeks screening visit, may be re-screened until such time that they meet exclusion criteria or they reach 34weeks' gestation.

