# 5.9 Frequency of Labs

The timing of follow up labs is determined by the expected amount of time a participant should see an increase in hemoglobin. The hypothesis is that 1) intravenous (IV) iron therapy will increase hemoglobin more with IV iron than oral iron over a 4 week period, approximately 0.8 g/dL in the IV group and 0.5g/dL in the oral arm and 2) IV iron will improve anemia at the time of birth admission, 1.5 g/dL for IV iron and 1 g/dL for oral iron supplementation, the standard of careThe estimates are informed from a 2018 study which reflected a 1.5 g/dL increase in hemoglobin by time of delivery in the intravenous group.

The follow up and reassessment is further informed by Micheal Auerbach's et al approach to treatment of IDA in pregnancy.

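### In IV women given two infusions, the 4-week primary hemoglobin is nominally drawn 31-36 days after first treatment, against 28 days in the oral arm: a small shift toward IV if hemoglobin is still rising

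*Combined protocol and SAP*

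**What the plan says.** The two arms use different starting points for the follow-up draws. For IV, section 6 (After randomization) says "follow up labs will be performed at 4 and 8 weeks after completion of infusion/s". For oral iron, it says "For the oral iron group, it will be drawn 4- and 8-weeks post initiation of treatment". Section 1.1.2, item h, makes the same split ("labs at 4 and 8 weeks post-initiation of pill for standard group and post-treatment of intravenous iron in the active group"), as does section 5.6 ("Labs will be drawn 4 and 8 weeks post-initiation (Oral iron)/ post treatment (IV iron"). Sections 7.1, 7.2, 7.7 and 7.9.1 and the visit table after section 7.3 follow it too. Some of these say completion for IV and others say only post-treatment.

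Dosing depends on baseline hemoglobin. At the higher level, "Women with Hgb 9-10.9 g/dL will receive one dose of 510 mg IV ferumoxytol". Women at 7-8.9 g/dL "will receive two doses of ferumoxytol 510 mg 3-8 days apart".

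Section 12.3 makes mean hemoglobin change over 4 weeks a primary outcome, alongside the change before delivery, and tests both by t-test. It mentions regression only for imbalance between arms, in the context of baseline characteristics. It states no adjustment for the day of the draw.

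Section 7.6 contains one general sentence that places the draws at 4 and 8 weeks from the start of therapy, without naming an arm.

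**The concern.** A change over 4 weeks should cover the same elapsed time in both arms. Here it does so for one-dose IV women, whose first and last infusions are the same. Two-dose IV women get 3-8 more days from first treatment to the draw than oral women of the same severity.

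If hemoglobin is still climbing after day 28, the extra days can act only in favour of the experimental arm, and an unadjusted t-test leaves them in the estimate. What is at stake is a small part of the 4-week treatment difference. Direction matters more than size, because the planned difference at that time is itself small.

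**Working it through.** The plan gives no figure for this offset, so there is none to reproduce. The nearest benchmark is its expected 4-week difference from sections 3.1 and 5.9: 0.8 - 0.5 = 0.3 g/dL.

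**Days from first treatment to draw**
- Oral, and one-dose IV: 28 days, and 56 days for the 8-week draw.
- Two-dose IV: 28 + 3 = 31 to 28 + 8 = 36 days. For the 8-week draw, which is not a primary measure, 56 + 3 = 59 to 56 + 8 = 64.

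**Slope after day 28**

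The plan expects 0.8 g/dL at 4 weeks and, in section 5.9, a "1.5 g/dL increase in hemoglobin by time of delivery in the intravenous group". The later rise is therefore 1.5 - 0.8 = 0.7 g/dL. Spreading it evenly from day 28 to birth needs two dates. For enrolment I use the preferred window in section 1.1.2 ("labs at 24-28 weeks gestation (preferred window, but may collect up to 34 complete weeks"). For birth I assume 39 weeks.
- Enrolment at 24 weeks: 15 x 7 - 28 = 77 days; 0.7/77 = 0.0091 g/dL per day.
- Enrolment at 28 weeks: 11 x 7 - 28 = 49 days; 0.7/49 = 0.0143 g/dL per day.

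**Shift per two-dose woman (slope x extra days)**
- Low: 0.0091 x 3 = 0.027 g/dL.
- High: 0.0143 x 8 = 0.114 g/dL.

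**Shift in the IV-arm mean (shift per woman x two-dose share)**

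The documents do not give the share with hemoglobin 7-8.9 g/dL; I assume 10-30%.
- Low: 0.10 x 0.027 = 0.0027 g/dL; 0.0027/0.3 = 0.9%.
- High: 0.30 x 0.114 = 0.034 g/dL; 0.034/0.3 = 11%.

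**Effect on the test**

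As an illustration, take 32 analysed per arm (40 x 0.8), an assumed SD of change of 0.8-1.0 g/dL, a 20% two-dose share and the same slope in both arms.
- The standard error of the difference is SD x sqrt(2/32), or 0.20-0.25 g/dL.
- The mean shift is 0.20 x 3 x 0.0091 = 0.0055 to 0.20 x 8 x 0.0143 = 0.023 g/dL, which is 0.02-0.11 standard errors.
- By the noncentral t distribution, the error in the tail favouring IV goes from 0.025 to 0.026-0.032. Total two-sided error goes from 0.050 to 0.0501-0.0515.

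**The case against.** The strongest defence is that each starting point suits its regimen. Oral iron continues until delivery, so it has no completion date before the draw, whereas IV iron is a finite course. Section 5.9 ties lab timing to when a response should be visible, so waiting 4 weeks after the full dose is coherent. That holds as a clinical reason. It does not make the elapsed times equal, and first dose is a treatment date that both arms have.

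A second defence is that real draw days will vary anyway. Sections 7.1 and 7.2 pair draws with prenatal visits where possible, and I found no day window for them in the text available. This variation may be as large as the offset. It affects both arms, however, so it adds noise without cancelling a difference that runs one way.

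A third is that the slope is weakly supported, and this stands. The 0.8 and 1.5 g/dL figures are arm-level expectations with different sets of citations, not two points on one curve, and they are not specific to women at 7-8.9 g/dL. The calculation is also unstable for late enrolment: at 34 weeks it gives 0.7/(5 x 7 - 28) = 0.1 g/dL per day, which is implausible.

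Three stronger readings are tempting, and the documents do not support them.
- A reader might infer a shift of up to 23% of the planned difference. That applies the average day 0-28 rate (0.8/28 = 0.0286) after day 28, with every gap at 8 days and a 30% share: 8 x 0.0286 x 0.30 = 0.069; 0.069/0.3 = 23%. It stacks three extremes, and nothing in the plan says that the early rate continues.
- A reader might infer a materially inflated false-positive rate. Even at that early rate, the illustration above gives a two-sided error of at most 0.056.
- A reader might infer from section 7.6 that the draw date is undefined. That sentence names no arm and does not override the arm-specific schedule. Staff who followed it literally would produce no offset.

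**Conclusion.** The offset is real but small. For two-dose IV women the nominal 4-week draw comes 3-8 days later after first treatment than for comparable oral women. This follows from the text alone.

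Its effect on hemoglobin is conditional. At the slopes implied by the plan's own expectations it is roughly 0.03-0.11 g/dL per two-dose woman and 0.003-0.034 g/dL in the IV-arm mean, or about 1-11% of 0.3 g/dL, in favour of IV. This rests on hemoglobin still rising after day 28 and on assumed values for the two-dose share, enrolment week and birth week. The shift is zero if hemoglobin has levelled off. One-dose women and the pre-delivery measure are not affected.

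This is a cheap improvement to the schedule. It does not threaten the trial's conclusions.

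**What to change.** Time the 4- and 8-week draws from first dose in both arms: first infusion or first tablet. Section 6 already times the symptom surveys from the start of therapy in both groups. State one window, the same for both arms, and record the dates of first dose and of each draw, so that a sensitivity analysis by draw day is possible. Align sections 1.1.2 (item h), 5.6, 6, 7.1, 7.2, 7.6, 7.7 and 7.9.1 and the visit table.

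The cost is wording and scheduling only; the number of draws does not change. The downside is that two-dose women would be measured 28 - 8 = 20 to 28 - 3 = 25 days after their last infusion instead of 28, so the IV effect may look slightly smaller.

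Randomization is not an equivalent origin. IV women need a scheduled infusion visit, and any delay in arranging it would also count against the IV arm.
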